### **4 Patient recruitment**

#### 4.1 Eligibility criteria

- 1) Age between 30-60 years
- 2) BMI range 30-40
- 3) Glycated haemoglobin (HbA1c) < 48 mmol/mol
- 4) Otherwise 'healthy' (based on medical history and screening blood samples)
- 5) Written and oral consent

#### 4.2 Study dropout

The occurrence of any condition necessitating withdrawal from the study, whether due to safety concerns, disease progression, subject choice, or non-adherence to protocol requirements, may serve as a reason for study withdrawal. Participants who withdraw will be replaced to reach the target enrollment as specified in the power analysis. The CONSORT flow diagram will present the timing, numbers, and reasons for withdrawals.

### **5 Statistical principles**

#### 5.1 Statistical thresholds

Confidence intervals (95%) and P values are two-tailed. A P value of  $<0.05$  is deemed statistically significant for all conducted analyses.

#### 5.2 Analysis population

All collected data from each participant will be analysed using a linear mixed effects model as specified in 6.1 Statistical methods. As this study aims to investigate the chronic and acute-on-chronic metabolic and cardiac effects of a novel lactate-ketone ester, certain modifications to the primary analysis may become necessary in a “modified Intention-to-Treat” approach. For instance, if a participant is unable to complete both study periods for reasons justified in the 4.2 Study dropout section their data will not be included in the final analysis.

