### *1.2 Hypothesis*

Being the first clinical trial in humans investigating LaKe, we hypothesize that the beneficial effects of circulating BHB and lactate observed in acute studies can persist with prolonged treatment. Thus, the primary hypothesizes are that a 28-day treatment with LaKe increases insulin sensitivity through the antilipolytic effects of BHB and lactate while enhancing cardiac output during acute-on-chronic intervention. The secondary hypothesizes are that 28-day treatment with LaKe compared with placebo: a) is safe and tolerable, b) decreases lipolysis, c) decreases fat and body weight, d) changes in the level of incretin hormones.

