### *2.3 Endpoints*

**Primary:** The study has two co-primary endpoints:

- 1) Between-treatment difference in cardiac output during acute-on-chronic intervention
- 2) Between-treatment difference in insulin sensitivity during acute-on-chronic intervention

**Secondary:** Between-treatment difference in:

- 1) Safety and tolerability: 10-item Beverage tolerability Questionnaire (BTQ)

- 2) Other echocardiographic parameters: Left ventricular ejection fraction, global longitudinal strain, left ventricular end-diastolic volume, left ventricular end-systolic volume, tricuspid annular plane systolic excursion, mitral inflow velocities (E and A), mitral plane velocities in the lateral mitral annulus (e' and s'), global work index (GWI)
- 3) Lipolysis
- 4) Body composition
- 5) Hormones and metabolites

**Exploratory:** Between-treatment difference in:

- 1) Lactate and BHB concentrations
- 2) Acid-base status
- 3) Biochemic 'safety': concentration measurements of CRP, sodium, potassium, leukocytes, thrombocytes
- 4) Validated questionnaires on appetite and mental well-being

**Timing of endpoints:** The primary and secondary endpoints are measured at each study visit following the 28-day treatment period.

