Secondary endpoints will be analysed and interpreted independently of the primary endpoint results and without adhering to a hierarchical testing sequence. The analysis methods for the secondary endpoints will mirror those outlined for the primary outcomes. No imputation will be performed for missing data.

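### The two-period completer exclusion in SAP 5.2 is not limited to efficacy, so on its most direct reading it also removes collected tolerability and safety data from participants who stop because of intolerance

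*SAP*

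**What the plan says.** - **Hypothesis (1.2).** LaKe has not been studied in humans before. Secondary hypothesis a) is that 28 days of LaKe, compared with placebo, "a) is safe and tolerable".
- **Endpoint (2.3).** The first secondary endpoint is "Safety and tolerability: 10-item Beverage tolerability Questionnaire (BTQ"), as a between-treatment difference. On timing: "The primary and secondary endpoints are measured at each study visit following the 28-day treatment period". Biochemical safety (CRP, sodium, potassium, leukocytes, thrombocytes) is exploratory, also as a between-treatment difference.
- **Withdrawal (4.2).** Any condition necessitating withdrawal, "whether due to safety concerns, disease progression, subject choice, or non-adherence to protocol requirements, may serve as a reason for study withdrawal". Those who withdraw are replaced until the target from the power analysis is reached. The CONSORT diagram gives timing, numbers and reasons.
- **Analysis population (5.2).** The section opens with "All collected data from each participant will be analysed using a linear mixed effects model". It then allows modifications to the primary analysis and gives an example, which concerns the final analysis: "if a participant is unable to complete both study periods for reasons justified in the 4.2 Study dropout section their data will not be included".
- **Secondary endpoints (6.1).** "The analysis methods for the secondary endpoints will mirror those outlined for the primary outcomes. No imputation will be performed for missing data".

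The SAP names no separate safety set, such as everyone who took at least one dose.

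**The concern.** For an efficacy endpoint, a completer rule raises the usual questions about missing data. For tolerability the problem is sharper, because the reason for exclusion can be the outcome itself. A participant who finds LaKe intolerable and withdraws meets a section 4.2 reason, loses their place in the final analysis and is replaced by someone else. The BTQ comparison then rests on people who got through both 28-day periods, and replacement brings the number back to 10, so nothing in the BTQ table shows that anyone is missing.

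At stake is one of the main claims a reader will want from a first human trial. If stopping is related to poor tolerability of LaKe, the error runs in one direction, towards concluding that LaKe is tolerable.

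**Working it through.** **1. The number that replacement refills.** Section 3 gives a difference of 30 % of 3.0 = 0.9 with SD 0.9 for insulin sensitivity, and 25 % of 5.6 = 1.4 with SD 1.4 for cardiac output. Both are a standardised difference of 1.0. A paired t-test at two-sided 5 %, taking the stated SD as the SD of the within-participant difference, has power 0.748 at n = 9 and 0.803 at n = 10. The stated 10 reproduces and is not in dispute here.

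**2. What the exclusion removes, by time of stopping.**

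| Participant stops | Collected at the post-period visits | Effect of 5.2 read directly |
|---|---|---|
| During period 1 | No 28-day BTQ | No 28-day score to delete; it is absent because of visit timing and no imputation |
| After or during period 2, before its visit | Period 1 BTQ and laboratory values | Collected values discarded |

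So 5.2 is responsible for the loss of data already in hand, mainly a completed period 1. It is not the cause of a 28-day score that was never taken.

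**3. How often this could matter.** The SAP gives no withdrawal rate. Assume each enrolled participant withdraws for intolerance with probability p and recruitment continues to 10 completers. Expected withdrawals are 10p/(1 − p), and the chance of at least one is 1 − (1 − p)^10.

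| Assumed p | Expected withdrawals | Chance of at least one |
|---|---|---|
| 5 % | 0.5 | 40 % |
| 10 % | 1.1 | 65 % |
| 20 % | 2.5 | 89 % |
| 30 % | 4.3 | 97 % |

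**4. Size of the shift in the BTQ difference.** Work in units of the SD of the LaKe-minus-placebo BTQ difference, assumed normal. If the k worst of N = 10 + k leave, the expected mean among the remaining 10 moves by (sum of the k largest expected normal order statistics)/10.

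- 1 of 11: 1.586/10 = 0.16 SD.
- 2 of 12: (1.629 + 1.116)/10 = 2.745/10 = 0.27 SD.

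These are worst cases, in which those who leave are exactly those with the worst differences. If the tendency to stop correlates 0.5 with the BTQ difference, halve them: 0.08 and 0.14 SD. The large-sample truncated-normal formula would give 0.18 and 0.30 SD, which is too high for samples this small.

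**5. Early stops as an outcome.** With 2 stops on LaKe among 12 exposed, the proportion is 2/12 = 17 % (exact 95 % CI 2 % to 48 %). With 1 among 11 it is 9 % (0.2 % to 41 %). Neither can be seen within a set of 10 completers, where the count of early stops is zero by construction.

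**The case against.** **The exclusion may be meant for efficacy only.** Section 5.2 opens by promising to analyse all collected data. The exclusion is an example of changes to the primary analysis that may become necessary, and its rationale is metabolic and cardiac effects. The mirroring sentence in 6.1 concerns methods, not populations. A sponsor could fairly say that BTQ data were always to be kept. This stands as far as intent goes: a reader might infer that the SAP expressly assigns tolerability to a completer set, and it does not. But the final analysis is unrestricted in 5.2, no other set exists, and the two sentences conflict. The analyst is left to choose after the data are seen. The extension to biochemical safety rests on the unrestricted wording alone, since the timing and mirroring sentences name only primary and secondary endpoints.

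**Withdrawals are reported.** They are: CONSORT will give timing, numbers and reasons. A reader might infer that intolerance would be hidden, which the SAP does not support. What is missing is a comparison of stops by treatment beside the BTQ result.

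**The protocol may provide for the rest.** A reader might infer that BTQ is taken only at the post-period visits, or that adverse events go unrecorded. Section 2.3 does not say only, and early-stop assessments and adverse-event reporting are commonly left to the protocol, which is not at hand. No finding is made on either.

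**A wider set cannot supply a score never taken.** Correct. It recovers only collected values, which is why early stops also need to be tabulated.

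**Conclusion.** The point holds as a defect of scope and internal conflict in section 5.2. On its most direct reading, the exclusion takes collected BTQ and biochemical safety data out of the analysis for participants who stop for intolerance, and replacement then restores the target number. The resulting tolerability comparison favours LaKe if stopping is driven by poor LaKe tolerability; if stopping is unrelated to tolerability, there is no such bias.

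The size depends on assumed withdrawal, because the SAP states none. With one or two such participants it is at most about 0.16 or 0.27 SD of the BTQ difference on average, and 0.08 or 0.14 SD at a correlation of 0.5. These figures measure the whole loss from selective stopping. Part of it comes from visit timing and no imputation, so correcting 5.2 removes only part. The co-primary analyses and the sample size are not affected by this point. It should be corrected before analysis, since tolerability is a named hypothesis and the remedy is cheap.

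**What to change.** In section 5.2:

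1. Limit the two-period completer exclusion to the efficacy endpoints, and reconcile it with the opening sentence on all collected data.
2. Analyse all collected BTQ and biochemical safety data from every randomised participant who took at least one dose, by treatment taken, including those later withdrawn or replaced. The mixed model in 6.1 accommodates single-period data. McNemar's test, the 6.1 fallback, uses only complete pairs, so if it is needed, describe the unpaired values beside it.
3. Report early stops by the treatment being taken (n/N exposed, exact 95 % CI) beside the BTQ result.
4. Report any BTQ collected at early stopping separately. Do not substitute it for the 28-day value, because it reflects shorter exposure and would change what is being estimated.

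The cost is a few sentences and one extra table. The tolerability result may look less favourable, and intervals for early stops will be wide at this sample size.

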### **6 Statistical plan**

#### 6.1 Statistical methods

The mean between-treatment ( $\pm 95\%$  CI) change in the primary endpoints of cardiac output (CO) and insulin sensitivity, as well as other single-time-point outcomes, will be analysed using a linear mixed-effects model with fixed effects for treatment and treatment sequence (order) and a random intercept for participant to account for within-participant correlation. Fixed effects will be estimated using a restricted maximum likelihood (REML) procedure and compared using the Kenward–Roger method. Estimated marginal means (EMMs) for treatment will be obtained from the fitted model, and pairwise between-treatment differences will be tested. For log-transformed outcomes, EMMs will be back-transformed to the original scale and reported as geometric means.

Analysis of temporal effects during the acute-on-chronic intervention (repeated-measures data) will be conducted using linear mixed-effects models with fixed effects for treatment, time, and their

interaction, as well as treatment sequence (order), and random intercepts for participant and for visits nested within participants. Fixed effects will be estimated using a restricted maximum likelihood (REML) procedure and compared using the Kenward–Roger method. Estimated marginal means (EMMs) for treatment will be obtained at each time point from the fitted model, and pairwise between-treatment differences will be tested at each time point. For log-transformed outcomes, EMMs will be back-transformed to the original scale.

Assumptions for the statistical analysis will be assessed through inspection of linearity, homoscedasticity, and normality of residuals using plots (residuals vs. fitted values, scale–location plots, and normal Q–Q plots). If violations occur, including significant skewness of residuals or outcome variables, data will be log-transformed and reported accordingly. To enable log transformation, a small constant will be added to all values if multiple observations of 0.0 are present in the dataset. For log-transformed variables, results will be displayed on a logarithmic scale, and between-treatment effects will be expressed as relative changes derived from the model outcomes. If neither the original linear mixed model nor the log-transformed linear mixed model can be applied, data will instead be analysed using McNemar’s exact test, assuming that order and visit have no effect, with a contextual cut-off applied for classification.

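### SAP 5.2 calls a two-period completers set modified intention-to-treat, contradicts its own opening sentence and leaves exclusions open; separately, the 6.1 models lack a period effect

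*SAP*

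**What the plan says.** - **SAP 5.2, opening sentence:** "All collected data from each participant will be analysed using a linear mixed effects model".
- **SAP 5.2, next sentences:** "certain modifications to the primary analysis may become necessary", under the label modified intention-to-treat. One case is then given, and only as an example: someone who cannot finish both periods. The consequence for that person reads: "for reasons justified in the 4.2 Study dropout section their data will not be included in the final analysis".
- **SAP 4.2:** any condition requiring withdrawal counts, "whether due to safety concerns, disease progression, subject choice, or non-adherence to protocol requirements, may serve as a reason for study withdrawal". Also: "Participants who withdraw will be replaced to reach the target enrollment". Timing, numbers and reasons for withdrawal go into the CONSORT diagram. Nothing is said about restoring the balance of the sequences on replacement.
- **SAP 2.3:** "The primary and secondary endpoints are measured at each study visit following the 28-day treatment period". The tolerability questionnaire (BTQ) is among the secondary endpoints.
- **SAP 6.1:** the model for single-time-point outcomes has "fixed effects for treatment and treatment sequence (order) and a random intercept for participant". The repeated-measures model adds time within the visit and its interaction with treatment. Neither names a period effect. Secondary endpoints follow the primary methods, and nothing is imputed.

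The SAP gives no withdrawal rate and no within-participant correlation.

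**The concern.** Three things in 5.2 do not fit together.

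1. The opening sentence and the exclusion cannot both hold for someone who is measured after period 1 and then leaves.
2. The exclusion is tied to reasons that cover practically every withdrawal, and those people are replaced. What remains is a completers set, and the label promises more than that.
3. Completion of both periods is given only as an example of modifications that may be needed. Other exclusions could therefore be chosen after the data are seen.

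At stake are period-1 clamp, echocardiography and BTQ values that were observed and are then thrown away. The contrast comes to depend on who stayed. The BTQ is the most exposed in principle: someone who scores LaKe badly in period 1 and then leaves loses that score, and the CONSORT diagram reports the reason but not the score.

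The missing period effect is a separate weakness of 6.1. It matters under the present rule and again if one-period records are kept.

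**Working it through.** **Inputs from SAP section 3.** Insulin sensitivity: 0.30 × 3.0 = 0.9, and 0.9 / 0.9 = 1.0 SD. Cardiac output: 0.25 × 5.6 = 1.4, and 1.4 / 1.4 = 1.0 SD. Two-sided 5%, power 80%, n = 10.

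**The plan's own figure.** A paired t-test with the stated SD taken as the SD of the within-person difference gives 80.3% power at n = 10 and 74.8% at n = 9. So n = 10 reproduces. If the stated SD is the between-person SD, this corresponds to a correlation ρ of 0.5. The standard error (SE) is √(2 × 0.5 / 10) = 0.316 SD.

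**Assumptions (not in the SAP).** Bivariate normal outcomes with variance 1, no true effect, ρ = 0.5 (range 0.3 to 0.7), known covariance, and the withdrawal patterns below. Let m = φ(c)/(1 − p) be the mean active value of those who stay when the lowest fraction p leave.

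**Case 1: 14% of the active-first sequence leave after a poor observed active value.** c = −1.080, m = 0.259.
- Completers, that sequence: (1 − ρ)m = 0.129. The other sequence: 0.
- No period term: weight 0.86/1.86 = 0.462, so bias 0.060 SD (0.084 at ρ = 0.3, 0.036 at ρ = 0.7).
- With a period term: weight one half, so bias 0.065 SD (0.091 to 0.039).
- All data: 0, because the value that drives leaving is in the model.
- Simulated type I error of the completers analysis at n = 10: about 5.4%.

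**Case 2: 8% or 16% of both sequences leave before the active visit, on a low active value never observed.** m = 0.162 or 0.290.
- Completers: (1 − ρ)m = 0.08 or 0.14 SD.
- All data: the placebo-first sequence gives (1 − ρ²)m = 0.121 or 0.217, the active-first sequence 0.081 or 0.145. The average is 0.10 or 0.18 SD.
- A period term does not change this.

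**Period effect left out of 6.1.**
- *5+5 completers.* The estimate is unbiased, but the period effect goes into the residual. For 0.5 SD the expected variance of the differences is 1 + 0.5² × 10/9 = 1.28 instead of 1. Simulated power is 72.0% without the term and 79.0% with it; type I error without it is 3.0% instead of 5%.
- *6+4 completers.* (6 − 4)/10 = 20% of any period effect enters the treatment contrast.
- *5+5 plus two period-1-only people in one sequence.* That sequence's contrast has variance (1 − ρ)²/7 + (1 − ρ²)/5 = 0.1857; the other has 2(1 − ρ)/5 = 0.2. The inverse-variance weights are 0.5185 and 0.4815, so 3.7% of a period effect enters (5.3% at ρ = 0.3, 2.2% at ρ = 0.7). With the term it is 0.

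**Precision from keeping the two records, with a period term.** Variance (0.1857 + 0.2)/4 = 0.0964, against 0.100 for completers. The 95% CI half-width is 2.306 × √0.0964 = 0.716, against 2.262 × √0.100 = 0.715 (8 and 9 df assumed). There is no gain.

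**The case against.** The rule is not hidden. The operative sentence follows the label directly, withdrawals will be shown with reasons, and analysing only people with both periods is a recognisable choice in a small crossover. Replacement restores 10 completers, so planned power is kept. People who leave for poor tolerability may well do so during active treatment, before its visit. That is case 2, where the all-data set does slightly worse and cannot recover a BTQ score that was never taken. Naming the set correctly and closing the list would cure the wording without changing the primary analysis.

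Most of this stands. It limits the point to wording, open exclusions and needless loss of observed values. It does not remove the conflict with the opening sentence of 5.2.

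Three stronger readings are tempting and not supported:
- *The completers rule seriously biases the co-primaries.* The sizes found are small beside an SE of 0.32 SD, and the SAP gives no withdrawal rate from which to derive more. No size can be given for the BTQ.
- *All data must be primary because it is less biased.* That is true in case 1 and false in case 2.
- *A period effect is needed only if one-period records are kept.* It also costs power with 5+5 completers, and it biases the estimate if replacement leaves the sequences unequal.

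One could also argue that order in 6.1 already means period. But 6.1 ties order to treatment sequence, and its fallback test names order and visit as separate assumptions.

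**Conclusion.** The point holds on the text: 5.2 contradicts itself, mislabels a two-period completers set and leaves the exclusions open. Confidence in that is high. The numerical effect on the co-primaries is small: about 0.06 SD (0.04 to 0.09) in case 1 against a design difference of 1.0 SD. In case 2 the order reverses, 0.10 to 0.18 SD for all data against 0.08 to 0.14 SD for completers at correlation 0.5. These sizes rest wholly on assumed withdrawal patterns, correlation and known covariance.

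The missing period effect can weigh more. It costs about 7 points of power for an assumed 0.5 SD period effect with 5+5 completers, and lets 20% of any period effect into the contrast at 6+4. The size of any real period effect is unknown. Both matters should be fixed before unblinding.

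**What to change.** 1. **Period.** Add a fixed period effect to both 6.1 models, whichever analysis set is used. Cost: one degree of freedom; if there is no period effect, power at n = 10 goes from 80.3% to about 79%.
2. **Section 5.2.** Reconcile the opening sentence with the exclusion. Delete the open wording, list every exclusion in full before unblinding, and call the two-period set completers rather than modified intention-to-treat.
3. **Two analyses.** For the co-primaries and the BTQ, report the mixed model on all randomised participants with at least one post-treatment measurement beside the completers analysis. State in advance which is primary; all data is the choice that follows the opening sentence of 5.2. Replacements should add to those who withdrew, not displace them from the all-data set.
4. **Limit.** State that neither set corrects for withdrawal before the active measurement.

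The cost is SAP wording, one model term and one extra analysis, with slightly unbalanced data in the all-data set. No participants or procedures are added.

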#### 5.3 Screening

For all screened participant the following will be presented: the total number of patients screened, the count of screened patients not recruited, the number of patients successfully recruited, and the rationale for non-recruitment. The count of screened patients are individuals excluded before the screening visit and those excluded between the screening visit and randomization; they will be presented in a detailed summary.

